# Table 8: Probability of observing at least one event for a range of true event rates based on a sample size of n=30 subjects

## 11.3. Final Analysis Plan

#### Analysis Populations:

All subjects who receive any amount of ZTI-01 will be included in the safety population. The pharmacokinetic analyses will be performed using the population of evaluable subjects. An evaluable subject is defined as a subject who receives all doses of ZTI-01, undergoes BAL at the randomized sampling timepoint with BAL return volume adequate for testing, and undergoes at least the one blood sampling timepoint that is concurrent with the BAL sampling timepoint, with blood sampling volume that is adequate for testing.

#### Safety:

The safety outcome measure will be the occurrence of AEs (Appendix B) at any time from the start of study drug administration through the end of subject follow-up.

All subjects in the safety population will be included in the safety analyses. AEs will be collected from the time of dosing on Day 1 through the Telephone Follow-Up Interview on Day 3. TEAEs will be tabulated by severity (mild, moderate, or severe), type (MedDRA system organ class and preferred term), and by the relationship to the study drug as assessed by the investigator. TEAEs will be summarized both by incidence and frequency. For summaries by incidence, subjects will be tabulated according to the most severe grade of AE experienced (each subject counted only once per type of AE). For summaries of

#### CONFIDENTIAL

DMID/NIAID/NIH

DMID Protocol 16-0058	Version 9.0
IV Fosfomycin PK Study	27 August 2020

frequency, each AE (by type) will be tabulated by severity, with each occurrence of the AE being counted (same subject can contribute multiple events to frequency). Tabulations of incidence and frequency will be performed separately for AEs overall and for related AEs only.

Observed and change-from-baseline vital signs, laboratory, and ECG data will be summarized using the mean, median, standard deviation, minimum, and maximum. The most recent measurement prior to start of infusion of the first ZTI-01 dose will be regarded as baseline. The number and percentage of subjects with laboratory, vital sign, and ECG abnormalities at baseline, subsequent visits, or early termination from the trial will be tabulated. The results of all laboratory tests, physical exam findings, ECGs, and vital signs will be presented in data listings.

Pharmacokinetics:

The pharmacokinetic outcome measures will be plasma and intrapulmonary PK of ZTI-01.

The following plasma PK parameters will be derived from the plasma concentration vs. time curves for fosfomycin after ZTI-01 administration. Noncompartmental analysis will be used to determine PK parameters, but other modeling techniques can be employed as needed. The below PK parameters will be estimated using Phoenix® WinNonlin® version 8.0 or later, and using plasma concentrations collected after start of the first and/or third doses.

- Maximum measured plasma concentration (Cmax)
- Observed and extrapolated area under the concentration versus time curve (AUC0-8; AUC0-12; AUC0inf)
- Time to peak concentration (tmax)
- Terminal elimination half-life (t1/2)
- Terminal-phase elimination rate constant  $(\lambda_z)$
- Volume of distribution (Vd)
- Clearance (CL)

PK parameters ( $C_{max}$ ,  $t_{max}$ , and AUC0-8) will be compared by dose and the accumulation ratio will be estimated using both  $C_{max}$  and AUC0-8.

Intrapulmonary PK of ZTI-01 will be derived as follows. Serum and BAL urea measurements will be used to estimate the volume of ELF recovered in the BAL samples. The ratios of ELF and AM concentrations of fosfomycin to simultaneous plasma concentrations will be calculated for each subject and summarized for each sampling time. The median concentrations of fosfomycin from the BAL sampling times will be used to estimate the population average AUC0-8 of plasma, ELF, and AM. The

DMID/NIAID/NIH

Version 9.0

27 August 2020

ratio of population average  $AUC_{0-8}$  of ELF-to-plasma and AM-to-plasma will be calculated to determine the percent penetration.

Specific details of pharmacokinetic analysis will be included in the study-specific pharmacokinetic analysis plan.

DMID/NIAID/NIH

CONFIDENTIAL

27 August 2020

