#### Table 5: ZTI-01 dose preparation guidelines

Each 1 g dose of ZTI-01 contains 330 mg of sodium. Due to the salt load of the formulation, sterile WFI will be used to reconstitute each ZTI-01 vial and to prepare the 200 ml ZTI-01 infusion (Table 6).

A total of two 4 g vials are required to prepare the 6 g dose. Deliver 20 mL of sterile WFI from the syringe into each vial containing 4 g of ZTI-01 powder to dissolve the powder. Always use sterile WFI and aseptic technique to reconstitute the powder. A slight degree of warming occurs when the powder is dissolved upon reconstitution of the vial, due to an exothermic reaction. After reconstitution, the product

```
DMID/NIAID/NIH
```

DMID Protocol 16-0058	Version 9.0
IV Fosfomycin PK Study	27 August 2020

will be used to prepare the infusion solution as follows, and as further detailed in the MOP: Using aseptic technique, withdraw an equal amount (15 mL) from each reconstituted vial (a total volume of 30 mL from both vials). The solution that is left in each vial will remain "unused." Add the 30 mL of diluted ZTI-01 to 170 mL of sterile WFI to yield the 200 mL total volume for infusion. The storage for the infusion bag, before administration, is limited to 4 hours at room temperature (20-25°C) or 24 hours at refrigerated conditions (2 - 8°C).

	Table 6: ZTI-01	(disodium	fosfomycin	) reconstitution	with	WFI
--	-----------------	-----------	------------	------------------	------	-----

Dose	Preparation Steps
	Step 1: Add 20 mL of sterile WFI to each of two vials of ZTI-01 powder
6 g	Step 2: Draw 30 mL total from both vials of diluted ZTI-01. Note: Draw an equal amount (15 mL) from each dissolved vial; the 5 mL left in the vials remain "unused."
	Step 3: Add the 30 mL of dissolved ZTI-01 to 170 mL of sterile WFI to yield the 200 mL total volume for infusion.

Note: The pharmacy will need to use/reconstitute 2 vials for each 6 g dose.

ZTI-01 should always be administered as a 200 mL infusion over 1 hour (+10 minute window).

Note: Each 1 g dose of ZTI-01 contains 330 mg of sodium; a 6 g dose of ZTI-01 contains 1980 mg of sodium. Each subject receiving 3 doses per protocol will be administered 5940 mg of sodium.

The ZTI-01 6 g infusion solution will be infused intravenously over 1 hour (+10 minute window) using an IV infusion pump at a rate set to 200 mL/hr. A dose will be administered every 8 hours for 3 doses.

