#### 8.2.2. Bronchoscopy and Bronchoalveolar Lavage (BAL)

Each subject will be assigned to one bronchoscopy sampling timepoint. The bronchoscopy sampling times will be at 30 minutes, 1 hour 15 minutes, 2, 5, and 8 hours from the start time of the third (last) infusion of ZTI-01. A total of 6 subjects will be assigned to each of the five BAL sampling times.

Sodium, potassium, magnesium, calcium, and phosphorus will be measured approximately 2 hours prior to each subject's bronchoscopy timepoint. Subjects with grade 2 or higher abnormalities (Appendix B) in these electrolytes will not receive any further study product and will not undergo bronchoscopy.

Bronchoscopy will be performed in a standardized fashion according to the MOP. Topical lidocaine will be applied to the upper airways to prepare subjects for bronchoscopy. If needed, 1.0% percent lidocaine

CONFIDENTIAL

DMID Protocol 16-0058	Version 9.0
IV Fosfomycin PK Study	27 August 2020

will be used in the lower airway. A fiberoptic bronchoscope will be inserted into the right middle lobe. Four 50-mL aliquots of sterile normal saline will be instilled into the right middle lobe and each specimen will be immediately aspirated and placed on ice. BAL samples for PK measures will be obtained  $\pm 15$  minutes from the subject's assigned sampling time. The start and stop times of BAL will be recorded on the eCRF.

Subjects will be continuously monitored during bronchoscopy. Blood pressure, heart rate, respiratory rate, and peripheral oxygen saturation will be recorded before and at the end of bronchoscopy. Subjects will undergo cardiac monitoring during bronchoscopy.

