#### 8.2.3. Pharmacokinetic Blood and BAL Samples

An assay to measure ZTI-01 concentrations in plasma, BAL, and cell pellet samples and urea in plasma and BAL samples will be conducted at a central analytical lab using a validated LC-MS/MS bioanalytical assay. Timing of samples will be with respect to the start of each dose of study drug (pre-dose and postinfusion start, when applicable). The date and time of each PK sample and BAL collection will be recorded in the eCRF. Blood PK samples will be drawn for all subjects within the following windows: -10 to -1 minute for scheduled samples at pre-dose;  $\pm 5$  minutes for scheduled samples at 30 minutes, 1 hour 15 minutes, and 2 hours; +0-5 minutes from end of infusion for the scheduled sample at 1 hour; and  $\pm 15$  minutes for scheduled samples at 5, 8, and 12 hours. BAL samples for PK (fosfomycin and urea assays) will be obtained within +/- 15 minutes of the assigned sampling time.

Instructions for collecting, processing, storage, and shipping of plasma, BAL, and urine samples will be provided in the MOP.

Blood and BAL samples are summarized in Table 7.

Study day	Dosing	Blood sampling times*	BAL sampling times §
Day 1-2 Dosing ZTI-01 6 g IV infusion over 1 hour (+10 minute window)		All subjects: Pre-dose (-10 to -1 minutes), 30 minutes (during the 1-hour infusion), and 1 hour, 1 hour 15 minutes, 2, and 5 hours after the start of the first dose	No sampling
	Second dose: ZTI-01 6 g IV infusion over 1 hour (+10 minute window)	All subjects: Pre-dose (-10 to -1 minutes)	No sampling
	Third dose: ZTI-01 6 g IV infusion over 1 hour (+10 minute window)	All subjects: Pre-dose (-10 to -1 minutes), 30 minutes (during the 1-hour infusion), and 1 hour, 1 hour 15 minutes, and 2, 5, 8, and 12 hours after the start of the third (last) infusion of ZTI-01	Each subject: Complete a single bronchoscopy with BAL at one of the five sampling times: 30 minutes (during the 1-hour infusion), 1 hour 15 minutes, 2, 5, or 8 hours from the start of the third (last) infusion of ZTI-01
Day 2 At Discharge	No further dosing	All subjects: 12 hours after the start of the third (last) infusion of ZTI-01	No sampling
* Blood PK samp	les will be drawn for all subjects	within the following windows: -10	to -1 minutes for scheduled

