- m PK blood samples will be collected at 15 timepoints: before (within 10 minutes) the first, second, and third doses of study drug, at 30 minutes (during infusion), 1 hour (within 5 minutes after the end of infusion), 1 hour 15 minutes, 2, and 5 hours from the start time of the first dose of ZTI-01, and at 30 minutes (during infusion), 1 hour (within 5 minutes after the end of infusion), 1 hour 15 minutes, 2, 5, 8, and 12 hours from the start time of the third (last) infusion of ZTI-01. Blood PK samples will be drawn for all subjects within the following windows: -1 to -10 minutes for scheduled samples at predose; +/- 5 minutes for scheduled samples at 30 minutes, 1 hour 15 minutes, and 2 hours; +0-5 minutes

DMID/NIAID/NIH

after end of infusion for the scheduled sample at 1 hour; +/- 15 minutes for scheduled samples at 5, 8, and 12 hours. Actual times for dosing and sample will be recorded.

n Bronchoscopy with BAL at 30 minutes (during the 1-hr infusion), 1 hr 15 minutes, 2, 5, or 8 hours from T0 (defined as the start time of the last [third] infusion of ZTI-01). BAL PK samples will be obtained within +/- 15 minutes of scheduled timepoint. Actual times for dosing and sample will be recorded.

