10.3. Definition and Estimation of Individual PK Parameters

PK parameters will be estimated through a NCA using Phoenix® WinNonlin® version 8.0 or later (Pharsight Corporation, Cary, NC) using plasma concentrations collected after start of the first infusion. Actual post-dose time will be used for the estimation of PK parameters instead of nominal time.

Phoenix WinNonlin[®] NCA will use the following settings to compute parameters from serum and pulmonary PK data:

- Linear Up Log Down calculation method
- Uniform weighting
- IV Infusion
- Lambda Z Acceptance Criteria
- \circ Rsq_adjusted ≥ 0.90
- \circ Span \geq 3.0 half-lives
- \circ Includes at least 3 timepoints after T_{max}

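### Lung-to-plasma ratios called simultaneous can pair samples up to 20 minutes apart; in the 30-minute group this can distort an individual ratio by about 30–40%

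*Protocol*

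**What the plan says.** Protocol 11.3 makes the paired ratio an intrapulmonary outcome: "The ratios of ELF and AM concentrations of fosfomycin to simultaneous plasma concentrations will be calculated for each subject". The ratios are then summarised at each sampling time. SAP 3.2 repeats this, and SAP Tables 41 and 42 report it.

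The two halves of the pair have different timing tolerances:

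- **BAL** (Protocol 8.2.3): "BAL samples for PK (fosfomycin and urea assays) will be obtained within +/- 15 minutes of the assigned sampling time".
- **Plasma** (Protocol Appendix A footnotes; SAP 4.5.2): plus or minus "5 minutes for scheduled samples at 30 minutes, 1 hour 15 minutes, and 2 hours". At 5, 8 and 12 h the plasma window is ±15 minutes.

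The third dose is "infused intravenously over 1 hour (+10 minute window"), so the 30-minute BAL falls during the infusion. On group size, Protocol 8.2.2 says: "A total of 6 subjects will be assigned to each of the five BAL sampling times".

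Evaluability (Protocol 11.3, SAP 6.3.2) requires a blood timepoint concurrent with the BAL timepoint but sets no maximum gap in minutes. SAP 10.4.3 refers to plasma at the corresponding BAL timepoint. SAP 10.3 has an actual-time rule, "Actual post-dose time will be used for the estimation of PK parameters instead of nominal time", but SAP 10.4.2, which defines the ratio summaries, does not carry it over. Listings 25 and 27 show actual times and flag only samples outside their window.

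**The concern.** A ratio described as simultaneous should use plasma from the moment of the lavage. Under these windows a compliant 30-minute pair could be a lavage at 45 minutes and plasma at 25 minutes, or a lavage at 15 minutes and plasma at 35 minutes. Neither would be flagged. Plasma rises steeply during the infusion, so the denominator would belong to a noticeably different concentration.

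The ratio is a stated outcome with only six subjects per time. Avoidable timing scatter is therefore visible in each summary, and a habit of starting lavages late or early would shift the whole group.

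**Working it through.** The documents give no figure for this timing error, so there is nothing of the plan's to reproduce.

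**Inputs from the documents.** One-hour infusion; "A dose will be administered every 8 hours for 3 doses"; BAL after the third dose; BAL window ±15 min; plasma window ±5 min at 0.5, 1.25 and 2 h and ±15 min at 5 and 8 h; six subjects per time.

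**Assumptions.** The documents state no half-life. I take 2–3 h as the main case and 1–5 h as the range, in a one-compartment model.

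**Error factor.** Let L be the lung concentration, b the actual BAL time and p the actual plasma time. The reported ratio is L(b)/C(p) and the simultaneous ratio is L(b)/C(b). Reported divided by simultaneous is C(b)/C(p). The lung value cancels, so against the ratio as the plan names it no lung model is needed. Reading the same factor as the error against the ratio at exactly 30 minutes requires the lung to track plasma.

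**Plasma during the third infusion** (up to a constant, t in hours, k = ln 2/half-life):

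C(t) = (1 − e^(−kt)) + A·e^(−kt), with A = (e^k − 1)(e^(−8k) + e^(−16k)) for carry-over from doses 1 and 2.

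**Half-life 2.5 h.** k = 0.2773 and A = 0.3195 × (0.1088 + 0.0118) = 0.0386.

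- C(0.25) = 0.06697 + 0.03597 = 0.10294
- C(0.50) = 0.12945 + 0.03356 = 0.16301
- C(0.75) = 0.18775 + 0.03131 = 0.21906

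With plasma on time, BAL at 15 min gives 0.10294/0.16301 = 0.63, which is 37% too low. BAL at 45 min gives 0.21906/0.16301 = 1.34, which is 34% too high.

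**30-minute group, one-compartment model:**

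| Half-life | BAL 15 min early / late, plasma on time | 20 min apart, both in window | Mean absolute error, uniform timing in both windows | Subjects off by >30% | SD of median of 6 from timing alone |
|---|---|---|---|---|---|
| 2 h | −41% / +37% | −47% / +58% | 20% | 25% | 13% |
| 2.5 h | −37% / +34% | −44% / +53% | 19% | 19% | 12% |
| 3 h | −33% / +32% | −40% / +48% | 17% | 13% | 11% |

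Under uniform timing the median factor is 1.00, so there is no systematic shift. If every 30-minute lavage ran 10 minutes late with plasma on time, C(40 min)/C(30 min) would inflate the ratios by about 21–25%.

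**Sensitivity.** For half-lives of 1–5 h, the 15-minute offset gives −24% to −45% and +23% to +39%. A 70-minute infusion changes the 2–3 h results by only one or two points. Five two-compartment examples with assumed parameters give −33% to −38% and +23% to +31%.

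**Other BAL times.** After the infusion C(t ± 0.25)/C(t) = e^(∓0.25k). At 2.5 h this is 0.933 or 1.072; for half-lives of 1.5–4 h the error is about 4–12%. At 5 and 8 h, where both windows are ±15 min, a compliant pair can be 30 minutes apart, which gives about 11–19% at 2–3 h. One caution: in the two-compartment examples a 15-minute offset at 1 h 15 gives +14% to +41% (early) and −11% to −20% (late), so 4–12% is specific to the one-compartment model there.

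**Effect of interpolation.** Take plasma at the BAL time by linear interpolation between the pre-dose, 0.5 h and 1 h samples. The residual error for BAL at 15 or 45 min is about 0.4–5% (one-compartment, 1.5–4 h). In two-compartment examples it is about 2% at 45 min and 8–21% at 15 min.

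**The case against.** **The wording may already cover it.** The plan says simultaneous, not nominal. Tables 41–42 use timepoints as column groups, the reference to the corresponding timepoint describes a box plot, and SAP 10.3 introduces its settings for serum and pulmonary data beside the actual-time rule. An analyst could read actual-time pairing into this. What stands is that scheduled-time pairing is the natural reading rather than an explicit instruction. No text tells the analyst how to obtain plasma at the lavage time.

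**A lagging lung.** If ELF equilibrates slowly, the true ratio changes during the infusion, and an interpolated ratio describes minute 15 or 45, not minute 30. With an assumed equilibration rate of 0.5/h and half-life 2–3 h, a 15-minute lavage with exactly matched plasma misses the 30-minute ratio by +40% to +46%, against −7% to −13% with nominal pairing. This is partly right. At about 1/h and faster, interpolation is on the whole closer. At any rate it gives the simultaneous ratio that the plan defines. The lag is a reason to show actual BAL times and keep both pairings.

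**Stronger readings to avoid.** A reader might infer that all 30-minute ratios are wrong by 30–40%; that figure belongs to a lavage at the edge of its window. A reader might infer bias; nothing in the documents says lavages run consistently early or late. A reader might infer that percent penetration is wrong by a similar amount. It is not computed from these ratios: Protocol 11.3 and SAP 10.3.2 derive it from AUC0-8 of median concentrations, and SAP 10.5 adds a population model. Off-schedule lavages do enter those medians, but the effect is small. If all six 30-minute lavages sat at the same window edge, composite lung AUC0-8 would move about 2–6% (half-life 1.5–4 h, lung tracking plasma, pre-dose value set to the 8-hour value).

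**A descriptive study.** There are no hypotheses or power calculations, and actual times are listed per subject. This limits the urgency but does not supply the missing rule.

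**Conclusion.** The point holds as a limited one. The window mismatch, and the absence of a gap limit or alignment rule for the ratios, are plain in the documents. The size is conditional on an assumed half-life of about 2–3 h: up to about 30–40% on an individual 30-minute ratio for a 15-minute offset, more at the 20-minute extreme, and typically 17–20% in either direction if timing is spread evenly within the windows. Measured against the exact 30-minute ratio, these figures also assume that the lung tracks plasma. The consequence is extra scatter in a median of six, or bias if timing is systematic. Other times are much less affected, with the reservation about 1 h 15 if there is a marked distribution phase. This is a cheap improvement, not a defect that threatens the study's conclusions.

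**What to change.** - In SAP 3.2 and 10.4.2, define each ELF/plasma and AM/plasma ratio against the subject's own plasma concentration interpolated to the recorded BAL time: linear while concentrations rise, log-linear while they fall. State which recorded time is used, for example the midpoint of the BAL start and stop times that Protocol 8.2.2 already requires.
- Report the actual BAL times with Tables 41–42.
- Keep scheduled-time pairing as a sensitivity analysis, because with a lung lag the interpolated ratio refers to the actual BAL time, not exactly to 30 minutes.
- Optionally, in SAP 10.3.2, place each group's median actual BAL time on the composite AUC0-8 axis. The effect there is small.

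**Cost.** A few sentences and a little code, by SAP addendum before data lock (SAP 15). No new samples are needed: each subject already has eight plasma samples around dose 3, from pre-dose to 12 h, which bracket every permitted BAL time. The downside is that ratios within a group will refer to slightly different actual times.

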# 12. SOURCE DOCUMENTS AND ACCESS TO SOURCE DATA/DOCUMENTS

DEPRU will maintain appropriate medical and research records for this study, in compliance with Section 4.9 of ICH E6 GCP, and regulatory and institutional requirements for the protection of confidentiality of subjects. As part of participating in a DMID-sponsored study, DEPRU will permit authorized representatives of DMID and regulatory agencies to examine (and when required by applicable law, to copy) clinical records for the purposes of quality assurance reviews, audits and evaluation of the study safety and progress.

Source data are all information, original records of clinical findings, observations, or other activities in a trial necessary for the reconstruction and evaluation of the trial. Examples of these original documents and data records include, but are not limited to, hospital records, clinical and office charts, laboratory notes, memoranda, evaluation checklists, pharmacy dispensing records, recorded data from automated instruments, copies or transcriptions certified after verification as being accurate and complete, microfiches, photographic negatives, microfilm or magnetic media, x-rays, and subject files and records kept at the pharmacies, laboratories, and medico-technical departments involved in the trial.

27 August 2020

# **13. QUALITY CONTROL AND QUALITY ASSURANCE**

Following a written DMID-accepted site quality management plan, DEPRU and its subcontractors are responsible for conducting routine quality assurance (QA) and quality control (QC) activities to internally monitor study progress and protocol compliance. The Site PI will provide direct access to all study-related sites, source data/data collection forms, and reports for monitoring and auditing by the Sponsor, and inspection by local and regulatory authorities. The Site PI will ensure all study personnel are appropriately trained and applicable documentations are maintained at DEPRU.

The DCC will implement quality control procedures beginning with the data entry system and generate data quality control checks that will be run on the database. Any missing data or data anomalies will be communicated to DEPRU for clarification and resolution.

DMID/NIAID/NIH

CONFIDENTIAL

